14. Timing of final analysis

All analyses will be conducted after completion of data collection for the trial. The statistician and PI will be masked to study condition during data collection, cleaning, and the primary effectiveness analyses. Secondary analyses examining mediators that relate to intervention group characteristics (e.g., BeThere Mechanism of Action, Group Cohesion) or require analysis of intervention midline assessment data will be conducted after effectiveness analyses are finalized to preserve masking.

15. Timing of outcome assessments

Data used for this study will be collected by research assistants at baseline, midline (BeThere session 5), endline (within 2-3 weeks following session 9 or approximately 10-12 weeks post-enrollment), and follow-up (12 weeks after completion of the final session or approximately 22 weeks post-enrollment). The midline assessment was only administered to the experimental (i.e., BeThere) group and not to the waitlist control group.

SECTION 4: STATISTICAL PRINCIPLES

16. Level of statistical significance

A significance level of $\alpha=0.05$ will be applied.

17. Adjustments for multiplicity

We do not plan to adjust for multiple testing.

18. Confidence intervals

Results will be presented as coefficients and 95% CIs.

19. Adherence and protocol deviations

Participant adherence to the intervention will be measured using intervention session attendance records. Completion of the intervention will be defined as having attended seven or more sessions. We will report the mean (SD) and median (IQR) number of sessions attended in the BeThere group.

Facilitator fidelity to the intervention will be measured using a fidelity checklist. We will report the mean (SD) and median (IQR) scores on the fidelity checklist as an indicator of trial implementation quality.

Any major deviations from the protocol will be reported in the main outcomes paper.

20. Analysis populations

The primary analysis will be conducted on the intent-to-treat sample, meaning that all participants will be included and analyzed as randomized. No enrolled participants were excluded from the main analytic sample. We will also conduct a per protocol analysis including waitlist control participants who completed all assessments and did not participate in any BeThere intervention components and only BeThere intervention participants who completed seven or more intervention sessions and did not drop out of the study.

SECTION 5: TRIAL POPULATION

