- **Mechanisms of Action:** Total score on a 5-item measure developed to assess hypothesized mechanisms for the BeThere intervention (e.g., relaxation techniques, stress and anger management, positive parenting practices). Mechanisms of action were assessed at baseline, midline, endline, and follow up.
- **Caregiver psychological distress (see above)**
- **Caregiver stress (see above)**
- **Caregiver wellbeing (see above)**
- **Parenting (see above)**

Implementation variables

- **Attendance:** Number of sessions attended (participant-level; range: 0-9)
- **Facilitator competence:** ENACT score (12 of 15 items) measured post-training/pre-implementation and during training. We will operationalize facilitator competence as the % of harmful (item score=1) and % of not harmful (item score=3-4) behaviors observed
- **Intervention fidelity:** Total score on BeThere fidelity tool (8-items) assessing the number of intervention components adequately implemented per session (Range: 72-216)

Study outcome measures and timepoints

Measures	Baseline	Randomisation	Midline*	Endline	Follow up	Ongoing
Caregiver						
Parenting (BPS)	X			X	X	
Psychological Distress (K10)	X		X	X	X	
Caregiver stress	X		X	X	X	
Psychosocial wellbeing (WEMWBS)	X		X	X	X	
Child wellbeing (KINDL)	X			X	X	
Group cohesion (GCS)			X	X	X	
Mechanisms of action (MOA)	X		X	X	X	
Child						
Parenting (BPS – Child Version)	X			X	X	
Psychosocial wellbeing (KINDL)	X			X	X	
Randomisation		X				
Adverse events						X

*Midline assessments administered to BeThere study arm only

27a. Analysis methods

Data Management

We will prepare both a long and wide final dataset. The long dataset will include a separate observation for each assessment. The wide dataset will include one observation per individual with variables for each assessment period. The final dataset will include the following variables:

- Community identifier
- Household identifier
- Individual identifier (caregivers, child)
- Allocation [masked: will be coded 0 or 1 without a label until primary analyses are complete]
- BeThere group number/identifier
- Assessment number/time point
- Assessment date
- Caregiver age
- Child age
- Caregiver gender
- Number of caregivers in the household
- Caregiver-reported parenting items and total score
- Child-reported parenting items and total score
- Caregiver psychological distress items and total score
- Caregiver stress items and total score
- Caregiver wellbeing items and total score

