- Caregiver-reported child psychosocial wellbeing items and total score
- Child-reported psychosocial wellbeing items and total score
- Group cohesion items and total score
- Mechanisms of action items and total score
- Fidelity
- Number of sessions attended (in BeThere Group only)
- Facilitator competence

More details about each variable and how it will be operationalized is described in the appendix.

We will review the data and perform the following quality checks prior to beginning the analysis: 1) identify and input (if possible) any missing data using imputation; 2) review the distribution of all variables to identify any outliers or potential data entry errors, including reviewing the distribution of outcomes at each time point; and 3) search for any data irregularities. Any identified issues will be reviewed and reconciled with the research team. Once the dataset has been cleaned, we will proceed with creating and coding the variables required to answer the primary and secondary objectives. The variables used in the final analysis are described in the table below.

Descriptive statistics

The distribution of baseline characteristics will be reported for the overall sample and stratified by study arm. For each primary and secondary outcome, a summary of results will be presented by trial arm for each time point. We will summarize trial implementation indicators (BeThere attendance, facilitator competence, intervention fidelity) using descriptive statistics. Appropriate summary statistics will be applied to describe demographic, parenting, wellbeing, and implementation measures: mean and standard deviation for all symmetric (non-skewed) distributed measures; median, 25th and 75th quartiles for

skewed distributions. QQ plots and histograms will be used to assess data distributions of continuous measures. Categorical outcomes will be described using both numbers and proportions (percentage).

Loss to follow-up, active withdrawals from the trial, active withdrawals from treatment only, departures from randomised treatment and the prevalence of serious adverse events will be reported at follow-up.

Primary Analysis

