The analyses outlined in this strategy will be pragmatic, based on ITT and will utilize all available follow-up data from all randomised participants. The trial statistician will be blinded to treatment allocation. The main statistical analyses will establish the effectiveness of BeThere over waitlist control by comparing the mean difference of total parenting score at endline post randomization (see appendix).

Primary outcome

The primary outcome is the total score of the parenting scale at endline. We will compare randomized groups at endline and follow-up adjusted for baseline total score of parenting scale and account for hierarchical clustering of caregivers at the level of household. Specifically, we will fit a three-level random intercept linear regression model considering observations from endline and follow up at level 1, household at level 2 and community at level 3. The model will include the total score parenting scale at endline and follow up as the outcome variables with treatment group, baseline rate of parenting total score as explanatory variables. A time by treatment interaction will be included to allow the effect to differ at each time point (endline, follow up).

Secondary outcomes

Secondary outcomes as listed will be assessed with a similar methodology for the primary outcomes, using generalized linear mixed models with the appropriate link function/distribution. Normal outcomes will use an identity link function, binary variables would use a logit link function, and Poisson (count) variables would use a log link function. We will use all available time points in the model and extract differences at endline and follow up post-randomisation. All the questionnaires to be used have validated methods of scoring.

Method for handling non-compliance

In addition to the primary intention-to-treat analysis the effect of actually receiving treatment as defined in the protocol will also be estimated using a per-protocol analysis (PP). The PP analysis will remove data of those who:
attended fewer than seven sessions and any participant who did not complete all study assessments.

Planned sensitivity analysis

As a sensitivity analysis, we will replicate the effectiveness models excluding Community #1: Tibek due to implementation issues and delays. We will conduct subgroup analyses for the effectiveness models

stratified by gender of the caregiver, number of caregivers in the household (1 vs. 2), and child age (3-7 years vs. 8-14 years).

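### Sections 20 and 27a define the per-protocol set differently, and neither version estimates the effect of treatment received that Section 27a claims for it

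*SAP*

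**What the plan says.** SAP Section 20 (Analysis populations) makes ITT primary and adds a PP analysis with a separate rule for each arm. From the control arm it takes "waitlist control participants who completed all assessments and did not participate in any BeThere intervention components". From the intervention arm it takes "only BeThere intervention participants who completed seven or more intervention sessions and did not drop out of the study".

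SAP Section 27a (Method for handling non-compliance) describes the PP set again, as a list of removals: those who "attended fewer than seven sessions and any participant who did not complete all study assessments". It also gives the purpose: "the effect of actually receiving treatment as defined in the protocol will also be estimated using a per-protocol analysis (PP".

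Three other statements bear on this. Section 19 sets the threshold: "Completion of the intervention will be defined as having attended seven or more sessions". Sections 15 and 26 both say: "The midline assessment was only administered to the experimental (i.e., BeThere) group and not to the waitlist control group". The dataset list in Section 27a limits the attendance variable to the BeThere arm, while Section 26 and the Appendix 1 codebook give it a 0 to 9 range and no code for waitlist caregivers. No adjustment for selection and no complier-average or instrumental-variable analysis is planned, and Section 29 lists no additional analyses.

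**The concern.** There are two separate problems.

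First, with two definitions and no statement of which governs, the PP set could be settled after results are seen. An SAP exists largely to prevent that.

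Second, attendance is decided after randomisation and is filtered in one arm only. Caregivers who reach seven sessions may differ from those who do not in stress, work or motivation. The waitlist arm contains both kinds of caregiver and cannot be split in the same way. The randomised comparison is lost, yet Section 27a presents the result as the effect of receiving treatment. A reader who takes that label at face value may treat the PP figure as a better estimate than the ITT one.

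**Working it through.** The plan states no figure for the PP analysis, so there is none to reproduce. The check has two parts.

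**1. Both rules applied to the same caregivers.** Section 27a is shown with waitlist attendance recorded as 0 or actual sessions (A), and with it blank so that the session rule is not applied to that arm (B).

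| Caregiver | Section 20 | 27a (A) | 27a (B) |
|---|---|---|---|
| Waitlist, 0 sessions, all assessments | keep | remove | keep |
| Waitlist, exposed to 3 sessions, all assessments | remove | remove | keep |
| Waitlist, exposed to 8 sessions, all assessments | remove | keep | keep |
| BeThere, 8 sessions, all assessments | keep | keep | keep |
| BeThere, 8 sessions, one missed assessment, not a dropout | keep | remove | remove |
| BeThere, fewer than 7 sessions | remove | remove | remove |

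Even under the charitable reading (B), the sections disagree on exposed waitlist caregivers and on BeThere attenders with one missed assessment. The latter disagreement would close only if a single missed assessment counted as dropping out, which Section 20 does not say. Completeness is itself ambiguous: with midline, BeThere has four scheduled assessments and the waitlist three; without it, both have three.

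**2. What the comparison estimates.** Let q be the share of the BeThere arm below seven sessions, g the amount (in SD, after baseline adjustment) by which such caregivers would score worse than attenders if untreated, μ the untreated mean of attenders, and d the effect in attenders. Leave aside any further selection from the completeness rule.

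- BeThere PP mean: μ + d
- Waitlist mean (both kinds of caregiver): μ − q·g
- PP difference: (μ + d) − (μ − q·g) = d + q·g

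The bias is therefore q·g. The SAP gives neither q nor g, so these values are assumptions:

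- q = 0.1, g = 0.1: 0.1 × 0.1 = 0.01 SD
- q = 0.3, g = 0.2: 0.3 × 0.2 = 0.06 SD
- q = 0.3, g = 0.3: 0.3 × 0.3 = 0.09 SD
- q = 0.4, g = 0.5: 0.4 × 0.5 = 0.20 SD

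If less well-placed caregivers attend more, g is negative and so is the bias.

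A simulation of 400,000 people (no clustering, no baseline covariate, no effect below seven sessions, no waitlist exposure) with q = g = 0.3 agrees with the algebra:

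| True effect in attenders | ITT | PP | ITT ÷ share attending seven or more |
|---|---|---|---|
| 0 | 0.003 | 0.095 | 0.004 |
| 0.30 SD | 0.213 | 0.395 | 0.304 |

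Under those assumptions, PP misses the effect in attenders by about q·g and the complier-type ratio recovers it.

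**The case against.** A reader might infer that Section 27a deletes the whole control arm, since waitlist caregivers attend no sessions. The document does not support that. Section 20 expressly keeps waitlist caregivers, Section 19 reports attendance for the BeThere group, and the dataset list holds attendance for that arm only, so no zero is established for the waitlist. The session rule was evidently meant for BeThere. This is loose wording to repair.

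A reader might also infer that both sections drop anyone with a missed assessment. Section 20 does so in the waitlist arm only.

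The bias figures rest wholly on assumed inputs. The effectiveness model adjusts for baseline score, which should absorb part of any prognostic gap, so g must be read as what remains. The direction is not known either. All of this stands, and no particular bias should be attributed to this trial.

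The complier-average alternative has its own assumption: no effect below seven sessions. Section 7 puts the caregiver mental-health content in the first four of nine sessions, so partial attenders may benefit. With 70% attending, an effect of 0.30 SD in attenders and 0.15 SD in the rest, ITT = 0.7 × 0.30 + 0.3 × 0.15 = 0.255, and 0.255 ÷ 0.7 = 0.364, which is 0.064 SD too high. That is as large as some of the PP biases above. Families share an arm, so a partner's attendance may also reach a non-attender. The added model is therefore a supplement with stated assumptions. It is needed only if the effect of treatment received is to be claimed.

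Finally, PP is secondary to ITT and nothing in the SAP gives it priority. That limits the consequence but does not reconcile the definitions or correct the label.

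**Conclusion.** The point holds on two counts. The two sections give different PP samples: they differ on the arm to which the session rule applies, on waitlist exposure and on completeness in the BeThere arm, and both leave the status of midline open. And the one-arm attendance filter does not estimate the effect of treatment received under either definition.

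The bias is q·g. Over q = 0.1 to 0.4 and g = 0.1 to 0.5 it runs from 0.01 to 0.20 SD, with the sign reversed if g is negative. These are assumed ranges; the SAP does not let the size or direction be determined for this trial. A reader might infer that the trial's main result is compromised. It is not: ITT is primary and PP selection does not enter it. The matter should be corrected, but the primary conclusion does not depend on it.

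**What to change.** 1. Put one arm-specific PP definition in both sections. Apply the seven-session rule to BeThere only, state the exclusion for waitlist exposure and name the variable that records it. Require the same named assessments in both arms: baseline, endline and follow-up, not midline. Copying Section 20 unchanged would not do, because it would keep the completeness rule in one arm only.
2. Label PP as descriptive and remove the claim that it estimates the effect of treatment received.
3. If that effect is to be estimated, add a supplementary complier-average analysis: two-stage least squares with randomised arm as instrument for attending seven or more sessions (or for number of sessions), baseline score and community as covariates, household-clustered standard errors, and all randomised caregivers with an outcome.
4. Keep ITT as primary.

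Cost: SAP wording for items 1 and 2. Item 3 adds one model, or two if both versions of attendance are used, from attendance data already in the dataset. Its price is a wider interval and assumptions that must be stated: no effect below seven sessions (or a linear dose-response if sessions are counted), no spillover from a partner's attendance, and how waitlist exposure is handled.

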THE KEY INGREDIENTS OF SUPPORTING CONFLICT-AFFECTED CAREGIVERS: A RANDOMIZED CONTROLLED TRIAL WITH MEDIATION ANALYSIS

Analysis Plan, Version 1.0

September 21, 2025

SECTION 1. ADMINISTRATIVE INFORMATION

1. Title and registration

The key ingredients of supporting conflict-affected caregivers: A randomized controlled trial with mediation analysis. This trial was registered on ISRCTN on January 27, 2025: ISRCTN89294864.

2. SAP Version: 1.0, September 21, 2025

3. Protocol version: 1.0, August 13, 2024

4. SAP revisions

None

5. Roles and responsibility

Statistician: [name]

Investigators: [name] [name], [name], [name], [name], [name], [name],

6. Signatures of person writing the SAP, senior statistician responsible, and chief investigator/clinical lead

Reviewed by all listed authors and signed by the following.

Name	Signature	Date
[name]		21/09/2025
[name]		21/09/2025
[name]		21/09/2025
[name]		17/9/2025
[name]		21/09/2025
[name]	[name]	16/09/2025
[name]		21/09/2025

SECTION 2. INTRODUCTION

This statistical analysis plan describes procedures for analyzing data from a randomized waitlist-controlled trial of the BeThere intervention on parenting in South Sudan. Relevant study design details are provided below followed by a detailed description of the statistical analysis approach. This analysis plan only covers the quantitative data analyses and excludes the qualitative analysis approach. Analyst and PI will remain masked to study condition until primary analyses have been completed.

The analyses described below will inform the development of two scientific manuscripts: 1) Effectiveness of the BeThere intervention on primary and secondary outcomes; and 2) Mediators of the effects of the BeThere intervention on child wellbeing and caregiver outcomes.

7. Background and rationale

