21. Screening data

There were no diagnostic or clinical screening criteria for admission into the study.

22. Eligibility

The study aimed to enroll 960 caregivers and 400 children in Bor Country, South Sudan. Families were randomized to the BeThere intervention or waitlist control with 1:1 allocation and it is possible that more than one caregiver per family participated in the intervention. Randomization at the family-level ensured that caregivers from the same family were allocated to the same study arm. Individuals were eligible for the trial if they were:

- 1) Primary caregivers of children aged 3-14 years;
- 2) fluent in Dinka;
- 3) Living in Pariak, Ghoi, Taragok, Tibek, or Lenguet communities in Bor Country, Jonglei State, South Sudan; and 4) Willing to participate and commit to all nine sessions of BeThere.

For households with more than one caregiver, all caregivers must be willing to participate in order to be included. Individuals were excluded if they were less than 18 years of age, had participated in either a parenting or stress management intervention within the last six months, did not have a child aged 3-14 years, were unable to complete the assessment, were not fluent in Dinka, or were unwilling to give informed consent. One index child per household was randomly selected. If the selected index child was 7-14 years of age, they were also enrolled in the study and completed child-reported assessments at baseline, endline, and follow-up. If the index child was between 3-6 years of age, they did not complete an assessment. However, their caregivers were still enrolled and participated in study assessments. Not all households had more than one caregiver and/or an index child between the age of 7-14 years who agreed to participate.

[figure not shown]
23. Recruitment

Participants were recruited through community-based organizations, chiefs, and existing networks with whom War Child had established relationships. Recruitment methods included flyers, awareness sessions, door-to-door outreach, and word of mouth, and continued until the target of 192 participants per location was reached. Strategies used successfully in the pilot RCT were applied to engage male caregivers, such as scheduling around income-generating activities and tailoring messaging to their interests.

24. Withdrawal and loss to follow-up

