- **Parenting (caregiver-reported; primary outcome(s)):** Total score on a 24-item parenting scale developed to assess change in parenting. The total score combines subscales assessing parental warmth and sensitivity (17 items) and harsh parenting (six items). Parenting was assessed at baseline, endline, and follow up. Caregiver-reported parenting at endline will be considered the primary effectiveness outcome for the study.

Secondary outcomes

- **Parenting (child-reported; secondary outcome):** Total score on a 24-item parenting scale developed to assess change in parenting. The total score combines subscales assessing parental warmth and sensitivity (17 items) and harsh parenting (6 items). Child-reported parenting was assessed at baseline, endline, and follow up. The child does not report separately on multiple caregivers.
- **Caregiver psychological distress (secondary outcome):** Total score on the 10-item Kessler Psychological Distress scale. Caregiver psychological distress was assessed at baseline, midline, endline, and follow up.
- **Caregiver stress (secondary outcome):** Total score on the 18-item caregiver stress measure developed by War Child. Caregiver stress was assessed at baseline, midline, endline, and follow up.
- **Caregiver psychosocial wellbeing (secondary outcome):** Total score on the 14-item Warwick-Edinburgh Mental Wellbeing Scale. Caregiver psychosocial wellbeing was assessed at baseline, midline, endline, and follow up.
- **Child psychosocial wellbeing (caregiver-reported; secondary outcome):** Total score on the modified 25-item Kiddy-KINDL for Parents measure evaluating wellbeing specifically among the index child. A modified version of the KINDL for Parents was used that combines the Kiddy-KINDL (3-6 years) and Kid-KINDL (7-13 years) into a single measure. Child wellbeing was assessed at baseline, endline, and follow up.
- **Child psychosocial wellbeing (child-reported; secondary outcome):** Total score on the modified 25-item Kid-KINDL for Children. This measure is completed by index children ages 7-14 years only. Child psychosocial wellbeing was assessed at baseline, endline, and follow up.

Mediators

- **Group cohesion:** Total score on the 7-item Group Cohesiveness Scale. Group cohesion was assessed at midline, endline, and follow up.

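### The subgroup analyses are planned as separate strata with no treatment × subgroup estimate, and for child-reported outcomes the 3-7 stratum can hold only 7-year-olds

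*SAP*

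**What the plan says.** Under Planned sensitivity analysis in SAP section 27a: "We will conduct subgroup analyses for the effectiveness models". The three factors and the method follow: the analyses are to be "stratified by gender of the caregiver, number of caregivers in the household (1 vs. 2), and child age (3-7 years vs. 8-14 years".

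The reach of the effectiveness models follows from the SAP's Introduction, which describes the first paper as "Effectiveness of the BeThere intervention on primary and secondary outcomes". Section 26 lists two child-reported measures among the secondary outcomes: parenting and psychosocial wellbeing.

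The only interaction in the effectiveness analysis belongs to the primary model: "A time by treatment interaction will be included to allow the effect to differ at each time point". No treatment × subgroup term appears, and there is no rule for comparing strata and no exploratory label. The outcome table shell (Appendix 1, table 3) has no place for a subgroup or interaction result. Section 29 lists no additional analyses, and section 17 rules out multiplicity adjustment.

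On child age, section 22 says: "If the selected index child was 7-14 years of age, they were also enrolled in the study and completed child-reported assessments". For younger children: "If the index child was between 3-6 years of age, they did not complete an assessment". Section 26 says of the child-reported KINDL: "This measure is completed by index children ages 7-14 years only". No reason is given for cutting the subgroup between 7 and 8.

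**The concern.** Fitting the model separately in women and men, or in younger and older children, answers whether there is an effect within each stratum. It does not answer whether the effect differs between strata, which is the purpose of a subgroup analysis. With two stratum results and no estimate of their difference, the natural reading is that treatment works where p is below 0.05 and not elsewhere. That pattern can be frequent when the effect is the same in both strata.

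The age split adds a second problem. Children aged 3 to 6 give no self-report, so for child-reported outcomes the 3-7 stratum is a single year of age under a misleading label. It is set against a stratum spanning seven years of age. A significant older stratum beside a non-significant younger one would then mostly reflect numbers.

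**Working it through.** The SAP gives no sample size or power for any subgroup, so there is no stated subgroup figure to reproduce. Its overall figure is consistent: 2 × 425 = 850, and 850/0.9 is about 945, close to the target of 960 (5 × 192).

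**Inputs from the SAP:** two-sided alpha 0.05 and 425 caregivers per arm (section 11); 328 index children enrolled (section 11); 1:1 allocation (section 22).

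**Assumptions, because the SAP gives no values:** overall power, standardised effect d, stratum shares, and the share of 7-year-olds. Household clustering is ignored and normal approximations are used throughout.

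**1. Chance that exactly one stratum is significant when the effect is identical in both**

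With equal, independent halves, power per half is p = Φ(c × √0.5 − 1.960), where c = 1.960 + z(overall power). The chance of discordance is 2p(1 − p).

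- Overall power 80%: c = 2.802; p = Φ(1.981 − 1.960) = 0.508; discordance = 2 × 0.508 × 0.492 = 0.50.
- Overall power 90%: c = 3.242; p = Φ(2.292 − 1.960) = 0.63; discordance = 2 × 0.63 × 0.37 = 0.47.
- No effect anywhere: 2 × 0.05 × 0.95 = 0.095 per factor.

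Fixing the sample at 425 per arm instead (212.5 per arm in each half), p = Φ(d/√(2/212.5) − 1.960), with √(2/212.5) = 0.0970:

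| d (assumed) | Power, full sample | Power, each half | Exactly one significant |
|---|---|---|---|
| 0.2 | 0.83 | 0.54 | 0.50 |
| 0.3 | 0.99 | 0.87 | 0.22 |
| 0.4 | >0.99 | 0.98 | 0.03 |

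Independence is reasonable for number of caregivers and child age, which divide whole households. The gender strata can share couples; positive correlation within couples would lower the discordance somewhat.

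**2. The 3-7 stratum for child-reported outcomes**

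If ages 7 to 14 are evenly spread, 7-year-olds are 1/8 of the children: 328/8 = 41, or 20.5 per arm. The detectable effect at 80% power is 2.802 × √(2/n per arm).

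| Share aged 7 (assumed) | Children | Per arm | Detectable d | Power at d = 0.4 |
|---|---|---|---|---|
| 5% | 16 | 8.2 | 1.38 | 0.13 |
| 12.5% | 41 | 20.5 | 0.88 | 0.25 |
| 20% | 66 | 32.8 | 0.69 | 0.37 |

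With 10% loss the middle row has 18.45 per arm and a detectable d of 0.92. The 8-14 stratum then holds 328 − 41 = 287 children and has power 0.92 at d = 0.4. With a true effect of 0.4 in both strata, the chance that only the older one is significant is 0.92 × (1 − 0.25) = 0.69.

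**3. What the interaction estimate can deliver**

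For stratum shares f and 1 − f, the SE of the difference in effects is the overall SE × √(1/f + 1/(1 − f)), which is twice the overall SE when f = 0.5. For an interaction as large as the main effect, power is Φ(2.802/2 − 1.960) = 0.29 when overall power is 80%, and Φ(3.242/2 − 1.960) = 0.37 when it is 90%.

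**The case against.** The strongest reply is that nothing in the SAP says a subgroup effect will be claimed from one significant stratum. Subgroups are not among the objectives in section 8, they sit under a sensitivity heading, and section 18 commits to coefficients with 95% CIs. This stands. A reader might infer that the subgroup conclusions will be unreliable, but the document draws no such conclusions, and at d = 0.4 in the full caregiver sample discordant strata are rare (3%). What remains is that the stated method omits the one quantity that a subgroup analysis needs.

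Three further inferences are tempting and are not supported.

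- *That the 7/8 cut mixes two instrument bands in caregiver report.* Section 26 says the caregiver version "combines the Kiddy-KINDL (3-6 years) and Kid-KINDL (7-13 years) into a single measure", and Appendix 1 lists one 25-item caregiver score. No separate bands remain to be mixed.
- *That the 7/8 cut contradicts the 6/7 boundary used elsewhere.* The 6/7 boundary decides who gives a self-report; the SAP does not present it as the age at which effects should change. For caregiver-reported outcomes, 7/8 is unexplained but usable, and moving it is a preference.
- *That splitting couples by gender breeds false differences between men and women.* Partners share an arm, so their stratum estimates may covary. The variance of the difference is V(women) + V(men) − 2Cov. Ignoring a positive covariance overstates it, which is conservative.

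**Conclusion.** The concern holds in a limited form. The plan specifies within-stratum analyses and no estimate of the difference in effect, so it does not show whether treatment effects vary. How often this misleads depends on an effect size that the SAP does not give in standardised form: about half the time if overall power is 80%, much less if power is very high. For the two child-reported outcomes, the younger age stratum is too small and too narrow to be informative across the whole assumed range of 5% to 20% aged 7. Severity is minor, because the primary analysis is unaffected and the SAP commits to no subgroup claim.

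**What to change.** Replace the separate strata with the full-sample mixed model, adding subgroup, treatment × subgroup and, because the model already lets the effect vary by time, the corresponding terms with time. Report the endline treatment × subgroup estimate with its 95% CI for each factor, with the stratum effects taken from the same model. State that the subgroups are exploratory and that no subgroup claim will rest on within-stratum p-values.

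Do not run the 3-7 versus 8-14 split for child-reported parenting or child-reported wellbeing. For caregiver-reported outcomes the cut may stay; one sentence giving its reason would help.

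This costs a change of SAP wording, best made while the statistician is still masked. The price in information is that interaction estimates are imprecise: with equal halves and 80% overall power, about 29% power for an interaction as large as the main effect. A wide interval should therefore not be read as evidence that effects are equal.
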